### **5.2. Randomization**

A web-based central randomization system developed by StrokeNet National Data Management Center (NDMC) and installed on the WebDCU™ Telerehabilitation Study website. Subjects will be assigned to one of the treatment groups according to the randomization scheme developed at the NDMC. Randomization will be done centrally using the WebDCU™ for all subjects entered in the trial. Covariate-adaptive randomization will be used to insure that values for (1) number of days post-stroke at time of randomization (2) FM score at the baseline visit, and (3) site are balanced across the two treatment groups.

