## 8. STATISTICAL CONSIDERATIONS, DATA ANALYSIS AND DATA MONITORING

In the study, populations used for testing comparable efficacy, the non-inferiority margin proposed for determining comparable efficacy, the statistical procedures used for summarizing and testing the primary and secondary comparable efficacy endpoints, and sample size justification for the proposed study. All analyses are two-tailed and use  $\alpha=0.05$ .

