### 8.3 Key covariates:

Key covariates to include in the data analysis model are based on established predictors in this setting: time post-stroke (number of days from stroke onset to randomization), severity of impairment (arm motor FM score at Baseline Visit), age, and enrollment site. Stroke subtype (ischemic vs. intracerebral hemorrhage) will also be included as a covariate.

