**Determination of sample size:**

The objective of this study is to assess comparable efficacy of telerehabilitation vs. in-clinic intensive arm motor rehabilitation therapy with respect to the mean  $\Delta_{FM}$  from the Baseline Visit to the 30 Day Follow Up Visit, using a non-inferiority margin of 2.05. Based on our pilot study, the mean  $\Delta_{FM}$  in the telerehabilitation group is expected to be 4.80 with SD=3.80; extension to multiple sites and enrollment of subjects at earlier time points post-stroke may be associated with larger variance, and so a SD=4.0 is assumed. Comparable efficacy will be established provided that the lower bound of the 95% confidence interval for the difference in the  $\Delta_{FM}$  between treatment groups is greater than -2.05. Assuming 80% power, the study will therefore seek to attain 30 Day Follow Up data on N=124 subjects (62 per arm). If the dropout rate is as high as 20%, then as many as 155 subjects may need to be enrolled.

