**8.5 Secondary outcome measures:****Stroke education**

- Gains in stroke knowledge from Screening Visit to Post-Therapy Visit, measured as the change in percentage of questions answered correctly on the Stroke Education Exam

In order to determine whether targeted educational material significantly increases subject knowledge related to stroke, the Stroke Knowledge Exam will be administered twice, once at the Screening Visit then again at the Post-Therapy Visit. A repeated measures ANOVA will be performed to determine if the percentage of Stroke Knowledge Exam answered correctly increases significantly from the Screening Visit to the Post Therapy Visit, controlling for days from stroke onset to randomization, initial Stroke Knowledge Exam score (at the Screening Visit), age, and enrollment site. To determine if gains in stroke knowledge vary according to the method by which stroke education is delivered, analysis will be repeated adding a time X group interaction term. Weight and blood pressure will be measured during the Screening Visit as well as during the Post Therapy Visit. In order to determine whether gains in stroke knowledge are associated with improvements in stroke risk factor control, the relationship between gains in stroke knowledge (the change in percentage of questions answered correctly on the Stroke Education Exam from the Screening Visit to the Post Therapy Visit) and improvement in weight and blood pressure control (change in weight, change in systolic blood pressure, and change in diastolic blood pressure) will be examined, controlling for days from stroke onset to randomization, Stroke Knowledge Exam score at Screening Visit, age, and enrollment site, and using a Bonferroni-adjusted alpha = 0.017; again, analyses will be repeated by adding a time X group interaction term.

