**Compliance and motivation.**

- Compliance with therapy, defined as the percentage of the 36 therapy sessions for which the subject completed assigned activities for at least 40 minutes

Compliance with rehabilitation therapy will be examined across all 36 sessions. For supervised sessions, a subject will be considered compliant if at least 40 min of assigned

therapy has been completed, determined from the therapist notes for subjects in the in-clinic group and from telerehabilitation system usage data for subjects in the telerehabilitation group. For unsupervised sessions, a subject will be considered compliant if at least 40 min of assigned therapy has been completed based on self-report for the in-clinic group and by telerehabilitation system usage data for subjects in the telerehabilitation group. To determine whether compliance with therapy differs according to treatment group, ANCOVA modeling will be used to examine compliance across the 36 sessions as a function of treatment group, controlling for days from stroke onset to randomization, age, and enrollment site. Secondary analysis will examine compliance with only the supervised therapy sessions, as well as compliance with only the unsupervised sessions.

**Motivation** (assessed along two independent dimensions):

- Activity-inherent motivation, defined as the change in score on the Physical Activity Enjoyment (PACES) Scale from baseline to end of the first week of therapy
- Consequence-related motivation, defined as the score on the Optimization in Primary and Secondary Control (OPS) Scale at the Baseline Visit

Activity-inherent motivation reflects how much a subject likes or dislikes an activity itself, independent of his or her commitment to the treatment goals. To measure this, the PACES Scale will be scored three times (at the Baseline Visit, after 3 supervised sessions, and after 18 supervised sessions). Activity-inherent motivation will be defined as the change in PACES score. Primary analysis will examine the change from baseline to end of week 1, while secondary analysis will examine change from baseline to end of week 6. To determine whether activity-inherent motivation is different for in-clinic vs. telerehabilitation therapy, ANCOVA modeling will examine differential change in PACES score between the two treatment groups, controlling for days from stroke onset to randomization, PACES score at the Baseline Visit, age, and enrollment site.

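### The between-arm models for knowledge, compliance and PACES adjust for two of the three randomization factors and omit baseline Fugl-Meyer; adding it is a free gain in precision

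*Combined protocol and SAP*

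**What the plan says.** Section 5.2 uses covariate-adaptive randomization on three factors. The first is days post-stroke; the plan wants this and "FM score at the baseline visit, and (3) site are balanced across the two treatment groups".

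Section 8.3 lists the key covariates as time post-stroke, "severity of impairment (arm motor FM score at Baseline Visit), age, and enrollment site", and then adds stroke subtype. The primary ANCOVA in the same section adjusts for days, baseline FM, age and site, so all three randomization factors are in it. The motor secondary endpoints in Section 8.4 follow the primary method.

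The between-arm models in Section 8.5 differ:

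- Knowledge: a repeated-measures ANOVA controlling for days, "initial Stroke Knowledge Exam score (at the Screening Visit), age, and enrollment site". The arms are compared by adding a time by group interaction.
- Compliance: an ANCOVA of "compliance across the 36 sessions as a function of treatment group, controlling for days from stroke onset to randomization, age, and enrollment site".
- PACES change: an ANCOVA controlling for days, "PACES score at the Baseline Visit, age, and enrollment site".

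None of the three lists baseline FM, and no reason is given. Section 8 states: "All analyses are two-tailed and use" a level of 0.05. Sections 1.2.2, 1.3.1 and 1.3.2 expect telerehabilitation to be comparable, or at least as good, on these outcomes. Section 8.5 tests for a difference and sets no margin.

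**The concern.** When allocation forces the arms to be alike on a variable that predicts the outcome, the true variance of the arm difference falls. A model that includes the variable sees this. A model that omits it leaves the variable's effect in the residual, so its standard error stays as large as if no balancing had been done. The interval is then too wide and the test runs below its nominal level.

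A link between arm severity and these outcomes is plausible, most clearly for compliance, which requires at least 40 minutes of assigned arm activity in a session. The usual comfort that a conservative test is safe does not carry over to these aims. With a comparability hypothesis, a difference test and no margin, a test with less power is more likely to return a non-significant result, and that result may be read as support for the hypothesis.

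**Working it through.** **Covariates set side by side**

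| Model | Days | Site | Baseline FM | Others |
|---|---|---|---|---|
| Randomization (5.2) | yes | yes | yes | – |
| Primary ANCOVA | yes | yes | yes | age |
| Knowledge (8.5) | yes | yes | no | age, screening exam score |
| Compliance (8.5) | yes | yes | no | age |
| PACES (8.5) | yes | yes | no | age, baseline PACES |

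**The plan's own figure.** The only sample size stated is for the primary endpoint: 124 (62 per arm), margin 2.05, 80% power, "and so a SD=4.0 is assumed". With a true difference of 0 (an assumption the plan does not state) and one-sided 0.025, n per arm = 2 × (1.96 + 0.84)² × 4.0² / 2.05² ≈ 60. The t-based version gives 61. Power at 62 per arm is 81.4% (normal) or 80.8% (t), and 124 / 0.80 = 155. So 124 is a sound N for the check below. No N, SD or power is given for knowledge, compliance or PACES.

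**Closed form, exact balance on FM.** Let r be the correlation of FM with the outcome after the other covariates. Standard error ratio = 1/√(1 − r²). Level = 2 × [1 − Φ(1.96/√(1 − r²))].

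- r = 0.1: ratio 1.005, level 4.9%
- r = 0.2: ratio 1.021, level 4.5%
- r = 0.3: ratio 1.048, level 4.0%
- r = 0.4: ratio 1.091, level 3.2%
- r = 0.5: ratio 1.155, level 2.4%

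A contrast with 80% power when adjusted has power 1 − Φ(1.96/√(1 − r²) − 2.80), which is 77%, 75% and 70% at r = 0.3, 0.4 and 0.5. Exact balance is the limiting case, so the levels above are a bound.

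**Simulation with realistic balance.** 4,000 trials of N = 124 with no true arm effect; minimization on days, FM and site with biased-coin probability 0.8; eight sites; FM uniform on 22–56 in three categories (cuts at 34 and 45); days uniform on 28–252 in three categories. The ANCOVA has arm, days, age and site, with and without FM. The algorithm, cut-points, equal sites and correlations are assumptions, because the documents give none of them. Outcome SD is 1.

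| r | Level without FM | Level with FM | Mean SE without | True SD without | Mean SE with | SE cut by adding FM |
|---|---|---|---|---|---|---|
| 0 | 4.7% | 4.8% | 0.1811 | 0.1819 | 0.1812 | none |
| 0.1 | 4.7% | 4.8% | 0.1811 | 0.1810 | 0.1803 | 0.4% |
| 0.2 | 4.7% | 4.8% | 0.1811 | 0.1786 | 0.1776 | 2% |
| 0.3 | 4.2% | 4.8% | 0.1812 | 0.1747 | 0.1729 | 5% |
| 0.4 | 3.5% | 4.8% | 0.1812 | 0.1692 | 0.1661 | 8% |
| 0.5 | 2.8% | 4.8% | 0.1813 | 0.1619 | 0.1570 | 13% |
| 0.6 | 2.1% | 4.8% | 0.1814 | 0.1527 | 0.1450 | 20% |

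Simulation error on a 5% level is √(0.05 × 0.95 / 4,000) ≈ 0.3 points, so 4.7% and 4.8% are not distinguishable. Under plain 1:1 allocation without balancing, the model without FM holds 4.9% at r = 0.5. The shortfall therefore comes from balancing on an omitted variable.

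**Knowledge needs a different repair.** Its arm contrast is the time by group interaction, which with two visits is the difference in mean change. A covariate entered only as a main effect is constant within a subject and does not alter that contrast. FM has to enter a model of the change score, or enter as FM by time.

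**The case against.** The omission can be read as a choice. In the primary model FM is also the outcome's own baseline value, and the knowledge and PACES models put their own baseline score in that slot. Section 8.3 speaks of one analysis model and stands directly before the primary-outcome text, so it may not govern Section 8.5. If it does govern it, FM is already prescribed and the matter is one of wording. This explains how the lists may have arisen. It does not meet the point, because the swap keeps FM's role as a baseline and drops its role as a balancing factor, and in compliance nothing replaces it.

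The size is also open to challenge. Eligibility restricts FM to 22–56, therapy is planned from each subject's Screening and Baseline data, and two of the models already hold the outcome's own baseline. Each could weaken the remaining correlation. This stands: the correlation may be small, and compliance is the strongest case of the three.

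A reader might infer that these analyses ignore how subjects were allocated. The documents do not support that, since days and site are in every model. A reader might also fear false-positive findings, but the omission raised the type I error at none of the correlations examined. Finally, the missing margin is a larger weakness for these aims than the missing covariate. That is fair, and adding FM does not cure it.

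**Conclusion.** The omission is certain, and so is the direction of its effect: where FM predicts these outcomes after the other covariates, standard errors are too wide and tests conservative. The size is not known. It is negligible up to a partial correlation of about 0.2, modest at 0.3 to 0.4 and material from about 0.5, under the minimization scheme assumed above. The documents give no correlation of FM with knowledge gain, compliance or PACES change, so a statement that the standard errors are materially wrong would go beyond them. Only these secondary comparisons are touched; the primary non-inferiority decision and N=124 are not. This is a free improvement, not a flaw that threatens the trial.

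**What to change.** In Section 8.5:

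- Add Baseline Visit arm motor FM to the compliance ANCOVA and the PACES ANCOVA.
- For the between-arm knowledge comparison, specify an ANCOVA of the change in exam score with arm, days, baseline FM, screening exam score, age and site. Alternatively, keep the repeated-measures model and add an FM by time term. FM as a main effect alone would do nothing for this contrast.
- If FM is left out on purpose, give the reason and state which models Section 8.3 governs.

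The cost is one degree of freedom per model and a few words in the plan. No new data are needed: FM is scored at the Baseline Visit before randomization and is an eligibility criterion, so it should exist for every randomized subject.

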### 1.3 Specific Aim 3. Patient Compliance with and Motivation for Therapy:

A major issue in rehabilitation therapy is patient compliance. Compliance and its variance across patients will be examined by measuring two dimensions of motivation. Aim 3 hypothesizes that compliance and activity-inherent motivation will be comparable across the two study treatment groups, and that compliance will vary with consequence-related motivation.

**1.3.1** Compliance with therapy, defined as the percentage of the 36 therapy sessions for which the subject completed assigned activities for at least 40 minutes, will be comparable or better with telerehabilitation as compared to compliance with in-clinic therapy.

**1.3.2** Activity-inherent motivation, which reflects how much a patient enjoys a therapy and defined as the change in score on the Physical Activity Enjoyment (PACES) Scale

from the Baseline Visit to end of the first week of therapy, will be at least as high (and in many patients higher) with telerehabilitation as compared to in-clinic therapy.

**1.33** Level of consequence-related motivation, which reflects the patient's degree of dedication to treatment goals and defined as the score on the Optimization in Primary and Secondary Control (OPS) Scale at the Baseline Visit, will emerge as a significant predictor of compliance in both groups, even after controlling for key variables. When consequence-related motivation is high, compliance will be high, for both treatment groups. When consequence-related motivation is low, compliance may be lower but will vary with the level of activity-inherent motivation.

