Consequence-related motivation reflects a subject's level of commitment to treatment goals. To measure this, the OPS Scale will be scored three times (at the Baseline Visit, after 3 supervised sessions, and after 18 supervised sessions). We hypothesize that across both treatment groups, the baseline level of consequence-related motivation (OPS score at the Baseline Visit) will predict compliance with rehabilitation therapy. Furthermore, we hypothesize that when consequence-related motivation is high compliance will be high for both treatment groups, however when consequence-related motivation is low compliance may be lower overall but will vary with the level of activity-inherent motivation. ANCOVA modeling will be used to determine if consequence-related motivation is a significant predictor of compliance with therapy (as defined above, across all 36 sessions), controlling for days from stroke onset to randomization, age, and enrollment site. Primary analysis will define consequence-related motivation using the OPS subscale that measures selective primary and selective secondary control striving (also referred to as goal engagement). Secondary analyses will define consequence-related motivation using the entire OPS score, and will also examine the effect of treatment group. An additional analysis will examine add the interaction term OPS x PACES to determine whether compliance varies with consequence-related motivation in a manner that depends on level of activity-inherent motivation; PACES and OPS scores will be centered and then combined in the interaction term.

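### Aim 3 expects baseline OPS to predict compliance in each group, but the primary model gives one pooled slope and no arm-specific slope is specified; a minor mismatch that a few sentences would close.

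*Combined protocol and SAP*

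**What the plan says.** Section 1.3 of the combined protocol and SAP (third item, printed as 1.33) states that baseline OPS "will emerge as a significant predictor of compliance in both groups, even after controlling for key variables". Section 8.5, under the motivation outcomes, words the hypothesis less strictly: "We hypothesize that across both treatment groups, the baseline level of consequence-related motivation" will predict compliance. It then adds that "when consequence-related motivation is high compliance will be high for both treatment groups".

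The analysis follows in the same paragraph: "ANCOVA modeling will be used to determine if consequence-related motivation is a significant predictor of compliance with therapy", with compliance taken over all 36 sessions, "controlling for days from stroke onset to randomization, age, and enrollment site". Those three are the only adjustment variables listed. The primary version uses the goal-engagement subscale of the OPS. Secondary analyses use the whole OPS score and "will also examine the effect of treatment group". The one interaction named for this hypothesis is with enjoyment: "An additional analysis will examine add the interaction term OPS x PACES".

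**The concern.** The aim, as worded in Section 1.3, is about each arm. The primary model fits one OPS slope to everyone, and that slope is a weighted average of the two arm slopes. It can differ clearly from zero when OPS predicts compliance in only one arm. The secondary look at treatment group does not settle the matter as written, because it names neither an OPS x group term nor a slope for each arm. A group main effect alone would not show whether OPS predicts compliance in each arm.

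Two features of the design make the missing group term more than a formality. Compliance with unsupervised sessions, 18 of the 36, is self-reported in the in-clinic arm and taken from system usage data in the telerehabilitation arm (Section 8.5). OPS is completed after randomization within the Baseline Visit (Section 5.3.2), so assignment is known when it is scored. Both variables could therefore differ by arm, and with no group term any such differences feed into the pooled slope.

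At stake is how one secondary result is described: as holding under both forms of therapy, or only on average.

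**Working it through.** **The plan's own figure.** The documents give no power or sample size for the OPS analysis. The only powered figure is for the primary endpoint: margin 2.05, SD 4.0, 80% power, two-sided alpha 0.05, 62 per arm. The normal formula gives 2 × (1.96 + 0.842)² × 4.0² / 2.05² = 59.8, so 60 per arm; the t-based version needs 61. The stated 62 is consistent with this, and 124 / 0.80 = 155 matches the dropout allowance. I use N = 124 below.

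**Inputs.** N = 124, 62 per arm (Section 8, sample size); two-sided alpha 0.05 (Section 8); covariates days, age and site (Section 8.5); 8 sites (the planning assumption in Section 12), which with days and age makes k = 2 + 7 = 9 adjustment terms. Assumed, because the documents give no values: the within-arm OPS-compliance correlation r, roughly normal compliance, and equal spread of both variables in the two arms.

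**Pooled slope when only one arm has an effect.** With equal arms, a correlation of r in one and 0 in the other averages to r/2. Approximate chance of a significant positive pooled slope: Φ(atanh(r/2) × √(N − 3 − k) − 1.96), with √(124 − 3 − 9) = √112 = 10.58.

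| r in one arm, 0 in the other | atanh(r/2) × 10.58 | minus 1.96 | Formula | Simulation |
|---|---|---|---|---|
| 0.2 | 1.06 | −0.90 | 19% | 19% |
| 0.3 | 1.60 | −0.36 | 36% | 36% |
| 0.4 | 2.15 | 0.19 | 57% | 57–59% |
| 0.5 | 2.70 | 0.74 | 77% | 77–78% |
| 0.6 | 3.28 | 1.32 | 91% | 89–91% |

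The simulations fitted the planned covariates with 8 site terms at N = 124; ranges are from separate runs. Adding treatment group as a main effect only gives 36%, 57%, 77% and 89% at r = 0.3 to 0.6, so that reading of the secondary analysis does not answer the per-arm question.

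**What per-arm slopes would do.** In the same one-arm-only settings (r = 0.3, 0.4, 0.5, 0.6), requiring both arm slopes to be significant and positive gives a both-groups statement in 1.5%, 2.6%, 3.7% and 3.3% of trials. An OPS x group test detects the difference in 39%, 59%, 79% and 93%.

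**What they cost when the effect is the same in both arms.** Per arm, ignoring covariates: Φ(atanh(r) × √(62 − 3) − 1.96).

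- r = 0.3: 0.310 × 7.68 = 2.38; 2.38 − 1.96 = 0.42; 66% per arm; 0.66² = 44% for both. Simulation with covariates: 40–42%.
- r = 0.4: 0.424 × 7.68 = 3.25; 3.25 − 1.96 = 1.29; 90% per arm; 0.90² = 81% for both. Separate covariate-adjusted simulation: 79%.
- Pooled slope: at r = 0.3, 0.310 × 10.58 − 1.96 = 1.32, so 91%; at r = 0.4, 0.424 × 10.58 − 1.96 = 2.52, so 99%.

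**The case against.** The strongest reply is that Section 8.5, next to the model, states a hypothesis that a pooled slope does test. Its wording is ordinary language for an average association, and its sentence about high motivation concerns the level of compliance, not a significant slope in each arm. This largely stands. It means the document carries two versions of one hypothesis; it does not make the pooled test wrong.

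Second, the planned look at treatment group may already include effect modification. The level difference between arms has its own ANCOVA in Section 8.5 with the same three covariates, so a repeat would add little. That is plausible. Against it, Section 8.5 names interactions where it wants them (time by group for stroke knowledge, OPS by PACES here), so an OPS x group term should not be presumed. The text is underspecified, which is a smaller fault than an omission.

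Third, at 62 per arm a pooled primary test is a sensible choice, and per-arm significance as the primary criterion would give up much power. With r = 0.3 in both arms, exactly one arm would be significant in about 45% of trials (2 × 0.66 × 0.34), inviting a false one-group reading. This stands, and it is why the pooled slope should remain primary.

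A reader might go further and infer that the trial will report a one-arm effect as holding in both. The documents do not support that: no rule turns the pooled p-value into a per-arm claim, and nothing indicates that the correlation is zero in either arm.

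**Conclusion.** The point holds as a minor mismatch between aim and analysis. A significant pooled OPS slope would support an average association; it would not by itself support the per-arm statement in Section 1.3, and the secondary analysis is not specified well enough to fill the gap. If OPS mattered in one arm only, the pooled slope would still be significant in about 19% (r = 0.2) to 91% (r = 0.6) of trials.

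These percentages are illustrations. They rest on assumed correlations, a correlation of exactly zero in the other arm, and roughly normal compliance. Pilot compliance was 97.9% (Section 3); a similar ceiling here would change the figures, including the per-arm power, but not the reasoning. The analysis is a predictor question within a secondary aim, and neither the Fugl-Meyer non-inferiority conclusion nor the between-arm comparison of compliance depends on it.

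**What to change.** In Section 8.5:

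1. Keep the pooled OPS slope as the primary test and add treatment group to that model.
2. State that the secondary analysis by treatment group includes OPS x group and reports the OPS slope with its 95% CI in each arm.
3. State that a both-groups conclusion will be drawn only if both intervals exclude zero. Otherwise report an average association, and do not read a non-significant arm as showing no effect there.
4. Bring the wording of Section 1.3 and Section 8.5 into line.

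The cost is a few sentences, with no new data and, in the settings simulated, almost no loss of power for the primary test from the added group term (90.5% without it and 90.4% with it at r = 0.3 in both arms). The real downside is that the both-groups statement becomes harder to earn: about 42% at r = 0.3 in both arms and 81% at r = 0.4, against 91% and 99% for the pooled slope. If the team does not want that, rewording Section 1.3 to an average association is enough.
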